23.	Economic Burden to Participants.....	27
24.	Informed Consent	27
25.	Setting.....	28
26.	Resources Available	28
27.	References	28
28.	Protocol Checklist	29

1. Study Summary

Project Title	Dose-Ranging Study of Persons Receiving Doxycycline
Project Design	To determine tissue pharmacology of multiple doses of doxycycline for sexually transmitted infection (STI) post-exposure prophylaxis (PEP), investigators at Emory University will collaborate with the Centers for Disease Control and Prevention (CDC) to conduct a clinical trial of up to 40 people aged 18-59 (at least 12 people assigned male sex at birth (AMAB) and 12 people assigned female sex at birth (AFAB)), with measurement of doxycycline concentrations in the rectum and vagina at study follow-up visits. Enrolled participants will take a total of 5 doses of doxycycline over a 3-week period.
Primary Objective	To determine dose-ranging tissue penetration of doxycycline for STI prevention strategies.
Secondary Objective(s)	N/A
Research Intervention(s)/Interactions	Doxycycline & Biological Specimen Collection
Study Population	Healthy people assigned male or female at birth and are willing to undergo study procedures.
Sample Size	40 participants total 
 • Arm A (100mg Doxycycline): at least 6 AFAB and 6 AMAB with a target sample size of 10 in each group • Arm B (200mg Doxycycline): at least 6 AFAB and 6 AMAB with a target sample size of 10 in each group
Study Duration for individual participants	8 weeks
Study Specific Abbreviations/Definitions	AFAB — Assigned female sex at birth AMAB — Assigned male sex at birth CDC — Centers for Disease Control and Prevention CRAI — Condomless receptive anal intercourse DOX — Doxycycline ED-PrEP — Event-driven pre-exposure prophylaxis HIV — Human Immunodeficiency Virus IDS — Investigational Drug Services MSM — Men who have sex with men PrEP — Pre-exposure prophylaxis PEP — Post-exposure prophylaxis STI — Sexually transmitted infection WHO — World Health Organization
Funding Source (if any)	Centers for Disease Control and Prevention

2. Objectives

The purpose of this study is to collect data regarding the ability of various oral doses of doxycycline to penetrate mucosal tissues in people AMAB and AFAB to inform future studies of combinations of doxycycline to protect against bacterial STIs.

3. Background

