Recent studies have demonstrated the potential utility of single-dose oral doxycycline post-exposure prophylaxis (Doxy-PEP) against bacterial sexually transmitted infections (STIs)^{1,2}. New dosing strategies are being explored that would allow for a single event-driven oral dose of medications that protect from HIV as well as other bacterial STIs. However, the ability of doxycycline to penetrate mucosal tissues and provide protection from STIs remains underexplored. A previous pilot study conducted by the DHP Laboratory Branch at CDC examined the ability of a 200mg oral dose of doxycycline to penetrate the vaginal and rectal mucosa. However, data regarding alternative doxycycline doses and accumulation of doxycycline with multiple doses are lacking^{1,2}.

The purpose of this project is to collect data regarding the ability of various oral doses of doxycycline to penetrate mucosal tissues in people AMAB and AFAB to inform optimization of doxycycline for STI prevention strategies. Results from this study will be compared to results of the previous pilot study conducted by the DHP Laboratory Branch at CDC. The objectives of this project are to conduct a clinical study investigating the pharmacokinetics of two different doses of doxycycline in people AMAB and AFAB where biological specimens are provided to the DHP Laboratory Branch for doxycycline measurement and analysis. Data regarding mucosal drug exposure will help inform development of STI prevention strategies.

Public Health Relevance: Incidence of bacterial STIs are increasing and studies have recently shown that Doxy-PEP can reduce incidence of bacterial STIs among men who have sex with men (MSM) and Doxy-PEP is being explored for STI prevention among women^{3,4}. A better understanding of mucosal drug penetration of doxycycline will inform the design of future studies to prevent STIs in various populations.

4. Study Endpoints

Primary Study Endpoints

1. To compare doxycycline concentrations in rectal tissues collected 24 hours after T¹ dose of 100 mg or 200 mg of doxycycline in AMAB participants.
2. To compare doxycycline concentrations in vaginal tissues collected 24 hours after T¹ dose of 100 mg or 200 mg of doxycycline in AFAB participants.
3. To compare doxycycline concentrations in rectal tissues collected 24 hours after T⁵ dose (visit 8) of 100 mg or 200 mg of doxycycline in AMAB participants.

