4. To compare doxycycline concentrations in vaginal tissues collected 24 hours after T⁵ dose (Visit 8) of 100 mg or 200 mg of doxycycline in AFAB participants.

Exploratory Endpoint

To assess longitudinal doxycycline concentrations in blood, urine, throat, vaginal, penile, and rectal secretions over the 3-week study period in people taking 5 doses of 100mg vs. 200mg of doxycycline.

5. Study Intervention/Investigational Agent

Study Product Description

Doxycycline is used to treat or prevent infections that are strongly suspected to be caused by bacteria; it is an antimicrobial drug indicated for bacterial infections such as sexually transmitted infections.

It will be purchased from the manufacturer and stored at the Emory Investigational Drug Services (IDS).

Dosage, Preparation and Administration of Study Product

[figure not shown]
Doxycycline (DOX) will be given orally at 100 and 200 mg doses. Pharmacy packages will be prepared by an IDS Pharmacist and delivered to the participant by a study team member. Prior to drug dispensing, the clinician will assess participant's medical history, and ensure the participant has no known allergies to the study drug. If a participant reports an allergy and a suitable alternative is not available, then the clinician may opt to not enroll the participant into the study.

Accountability Procedures for the Study Product

The IDS pharmacist will maintain accurate accountability logs at the Hope Clinic.

6. Procedures Involved

Study Schema

Study Visits

All study visits described below apply to both Arms A & B. The only difference between the two will be the dose participants receive (100 mg v. 200 mg). Study participants will be assigned to dosing arms in a sequential manner. Arm A will enroll at least 6 participants AFAB and at least 6 participants AMAB at 100mg prior to proceeding to Arm B. Target enrollment will be n=10 in each group. Arm B will enroll at least 6 participants AFAB and at least 6 participants AMAB at 200mg. Target enrollment will be n=10 in each group.

Recruitment

Potential participants will be identified from one of the recruitment methods (e.g., flyers, social media, advertisements, etc.) mentioned in the recruitment methods section below.

Phone Screening

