Vaginal and cervical tissue samples will not be collected in women who are menstruating, pregnant, or have possible cervical or vaginal infection. A pregnancy test will be administered to women of childbearing potential to ensure they are not pregnant. The first vaginal/cervical biopsy will be scheduled 7 to 10 days after their last menstrual cycle.

Twenty-four to forty-eight hours after the procedure, study personnel will call the participants who donated biopsy samples and inquire about symptoms, complications, or adverse events related to study procedures. Participants who report symptoms suggestive of any significant complications will receive advice on seeking care and will be given referrals to appropriate healthcare professionals as needed. This follow-up may be completed over the phone or through electronic communication.

Rectal Mucosal Sampling Procedures

A trained, delegated clinician will be performing all rectal mucosal sampling procedures with the assistance of the study coordinator utilizing a disposable anoscope, rigid sigmoidoscope, light source, and jumbo biopsy forceps.

Then, without the administration of any previous enemas or other preparation, a rigid sigmoidoscope will be inserted and 2-4 (first biopsy) or 8-12 (second biopsy) adequate ~1.0 mm thick biopsy specimens will be taken from normal-appearing rectal mucosa approximately 10 cm above the external anal aperture using flexible sigmoidoscopic forceps mounted on a semi-flexible rod. All biopsy specimens will be coded with a unique numeric identifier such that the laboratories that receive the specimens will be unable to link them back to the study participants. Two to three biopsy specimens will be placed immediately into cryotubes for testing of drug levels at CDC. The remaining biopsy specimens will be placed in media and transported to [name] lab where the specimens will be processed for various laboratory protocols (e.g., bulk and spatial transcriptomics, exogenous hormone treatment for bulk and spatial transcriptomics and explant challenge experiments, or flash-frozen for subsequent quantification of HIV within rectal tissue).

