Twenty-four to forty-eight hours after the procedure, study personnel will call the participants who donated rectal biopsy samples and inquire about symptoms, complications, or adverse events related to study procedures. Participants who report symptoms suggestive of any significant complications will receive advice on seeking care and will be given referrals to appropriate healthcare professionals as needed. This follow-up may be completed over the phone or through electronic communication.

Protocol Title: Doxy-PEP

Table 1. Study Schema – Arm A & B

	Screening Visit	Visit 1a	Visit 1b	Visit 2	Visit 3	Visit 4	Visit 5	Visit 6	Visit 7a	Visit 7b	Visit 8	Visit 9	Visit 10	Visit 11	Visit 12
Timepoint (Days)	-42 to 0	0	0	1	2	3	7	10	14	14	15	16	17	18	21
Timepoint (Hours)	-	0	2-4	24	48	72	168	240	336	338-340	360	384	408	432	504
Window	-	-	±2 hr	±2 hr	±2hr	±2 hr	±2hr	±2hr	±2hr	±2hr	±2hr	±2hr	±2hr	±72hr	±72hr
Informed Consent	X														
Physical Exam	X			X ¹							X ¹				
Medical History	X			X ¹							X ¹				
Current Medications	X			X ¹							X ¹				
Screening Labs ²	X														
Pregnancy Test	X			X							X				
Eligibility	X														
Dose Administration		X				X	X ³	X ³	X						
Biopsy				X							X				
Urine Sample	X	X		X	X	X			X		X	X	X	X	X
Rectal & Vaginal ⁴ Swab		X	X	X	X	X			X	X	X	X	X	X	X
Throat Swab		X	X	X	X	X			X	X	X	X	X	X	X
Urethral & Glans Swab				X		X					X		X		
Blood Volume	17 mL	10 mL	10 mL	10 mL	10 mL	10 mL			10 mL	10 mL	10 mL	10 mL	10 mL	10 mL	10 mL

¹Abbreviated/symptom-directed/review during non-screening visits.

²Includes CBC, coagulation, creatinine, HIV testing, urine, and self-collected swab for chlamydia & gonorrhea.

³Dose taken at home.

⁴Vaginal swabs done only on participants with vaginas.

7. Statistical Analysis Plan

Primary Outcomes

Comparisons between time points will be conducted with a non-parametric statistical test of differences in median doxycycline concentrations between the two dosing regimen arms, stratified by sex assigned at birth. P-values less than 0.05 will be considered significant.

Exploratory Outcomes

Exploratory outcomes will be analyzed with various statistical methods to examine changes over time in doxycycline concentrations between the dosing arms, stratified by sex assigned at birth.

8. Data and/or Specimen Banking

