Data and biological specimens collected for this study will be stored at the Hope Clinic. Identifiable data will be kept in a separate, locked cabinet at Hope Clinic and only accessible by MPIs and study staff. Electronic data will be stored in a secure database only accessible to study staff. Data and biological specimens will be stored with a unique study code number to maintain the blinding of the identity of the participant. After the study is completed, the de-identified, archived data and specimens may be stored for use by other researchers including those outside of the study. Only the PI and study staff will have access to a list that links a participants' unique study code to their identifiable information.

Leftover specimens from all study participants will be stored indefinitely and may be used for future use including laboratory assay development, unless a participant requests that specimens be destroyed or if required by IRB or other regulatory authority. Other use of specimens may apply to studies not covered by the protocol or the informed consent form for the main study.

De-identified data from this study may be placed into public databases where, in addition to having no direct identifiers, researchers will need to sign data use agreements before accessing the data. Any personal information that could identify participants will be removed or coded before the information is shared. Despite these measures, we cannot guarantee anonymity of participant personal data.

9. Sharing of Results with Participants

Study results, including results of laboratory tests, will not be shared with participants. If abnormalities deemed to be clinically significant are discovered during the procedure and/or from the safety labs, such as positive STI tests, these results will be discussed with the participant and a referral will be made to a primary care physician or specialist, as needed.

10. Study Timelines

- Participants will be considered on study for no more than 7 weeks .
- The duration anticipated to enroll all study participants is 1 years.
- This study is expected to take 2 years to complete.

11. Inclusion and Exclusion Criteria

Inclusion Criteria

1. Aged 18-59 years
2. Assigned male sex or female sex at birth
3. In good general health
4. Not currently taking doxycycline or other tetracycline-derived antibiotics and no plans to initiate during the study

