There is no anticipated direct benefit to participants.

19. Compensation to Participants

Participants will be compensated according to the schedule below:

- Screening Visit: \$50
- In Clinic Follow-Up Visits: $\$50 \times 10 \text{ visits} = \500
- Biopsy Visit: $\$100 \times 2 \text{ visits} = \200
- Total Compensation: \$750
- Optional Rectal Biopsy (Participants with Vaginas Only): $\$100 \times 2 \text{ visits} = \200
- Unscheduled/Drug Dispensation Visit (if needed): \$20

If they do not finish the study, they will be compensated for the visits they have completed. Participants may also receive an additional \$25 for peer referrals to the study if the peer referral enrolls in the study and identifies the enrolled participant as the referral source.

Compensation will be provided via Emory ClinCard.

20. Data Management and Confidentiality

The principal investigator, [name], will be ultimately responsible for receipt and transmission of the data and biospecimens. Biospecimens may be transported by local courier or shipping.

Participants will be assigned a unique study-specific identification number after they sign the consent form. All collected data and specimens will be associated with this number (excluding demographic intake forms). Data will be recorded on paper Case Report Forms (CRFs) and entered into a study-specific REDCap Database. Data entered in REDCap will only be linked to a participant by a unique study identification number. Paper forms will be

stored in a locked cabinet at Hope Clinic. Only study staff will have access to identifiable data.

Biologic specimens will be labeled with a unique study identification number at stored at the Hope Clinic prior to processing or shipment to another lab for assays. Laboratory staff will be unable to link the specimen identifier number with identifiable information.

Data and specimens will be stored indefinitely. However, once the IRB protocol is closed, deidentified electronic data will be exported from the REDCap database for long-term storage on Emory OneDrive. Paper records will be destroyed no sooner than 1 year after IRB close out.

Certificate of Confidentiality

Consistent with Section 301(d) of the Public Health Service Act, a Certificate of Confidentiality (CoC) applies to this research because this research is funded, conducted, or supported by CDC and the following is true:

The activity constitutes biomedical, behavioral, clinical, or other research; AND

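### Dose is assigned by enrolment order, 100 mg first and then 200 mg, so all four primary dose comparisons are confounded with enrolment period and possibly with assay batch

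*Combined protocol and SAP*

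**What the plan says.** Section 6 (Study Visits) sets the allocation: "Study participants will be assigned to dosing arms in a sequential manner". It then gives the order: "Arm A will enroll at least 6 participants AFAB and at least 6 participants AMAB at 100mg prior to proceeding to Arm B". The sample size entry in section 1 has the same minimum and target, "Arm A (100mg Doxycycline): at least 6 AFAB and 6 AMAB with a target sample size of 10 in each group", with matching numbers for Arm B. Section 6 also says that dose is the only thing that differs between the arms.

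Section 4 lists four primary endpoints, and each sets 100 mg against 200 mg. The first begins "To compare doxycycline concentrations in rectal tissues collected 24 hours after" the first dose, in AMAB participants. The others cover vaginal tissue in AFAB participants at the same time, and both tissues 24 hours after the fifth dose. Section 7 plans a non-parametric "test of differences in median doxycycline concentrations between the two dosing regimen arms, stratified by sex assigned at birth". It has no term for enrolment date or assay run. Section 12 limits demographic data other than sex assigned at birth to descriptive use.

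On timing, section 10 says "The duration anticipated to enroll all study participants is 1 years". On the assay, section 6 says of the rectal tissue "Two to three biopsy specimens will be placed immediately into cryotubes for testing of drug levels at CDC", and section 20 says that specimens are "stored at the Hope Clinic prior to processing or shipment to another lab for assays". The visible text describes no randomisation, gives no reason for the order, does not say whether Arm A places 7 to 10 may be filled while Arm B is open, and does not say how specimens are grouped into assay runs.

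**The concern.** The contrast between doses is the whole content of the primary endpoints. When dose follows enrolment order, anything that changes during the enrolment year changes with dose as well. Examples are the mix of people recruited, biopsy handling, storage time before assay and assay calibration. Part of such a change would be read as a dose effect, or would hide one. Stratifying by sex does not help, because the 100-mg-first order holds within each sex, and the plan has no other adjustment. A single drift could affect all four comparisons together, so agreement among them would not be reassuring.

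Estimates within one dose, such as the concentration reached at 100 mg, do not depend on how the arms were assigned. The concern is limited to the comparison of doses.

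**Working it through.** **The plan's own figure.** 2 doses × 2 sexes × 10 = 40 participants, as stated. The minimum is 2 × 2 × 6 = 24, or 12 per sex. The documents give no effect size, standard deviation or power.

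**How far apart the arms are.** Number the enrolment places within one sex 1 to 20 (target n = 10 per arm) and assume steady accrual over the stated year. The gap in months is (difference in mean place ÷ 20) × 12.

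| Schedule | Mean place, A | Mean place, B | Gap |
|---|---|---|---|
| No overlap | 5.5 | 15.5 | 10/20 × 12 = 6.0 months |
| Free mixing after the first 6 | 7.5 | 13.5 | 6/20 × 12 = 3.6 months |
| Arm A's last four enrolled last | 9.5 | 11.5 | 2/20 × 12 = 1.2 months |

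At 6 per arm only the no-overlap schedule is possible.

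**Assumptions for the size of the effect.** None of these is in the documents: log-normal concentrations, log-SD 0.4, 0.6 or 0.8, and a 1.5-fold change over enrolment, either gradual (log-linear) or as a single step. Section 7 names no test, so an exact two-sided rank-sum test is assumed. Its true size is 4.3% at 10 per arm (critical U = 23) and 4.1% at 6 per arm (critical U = 5).

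**Apparent 200/100 ratio when dose has no effect.**
- Gradual: 1.5^(difference in mean place ÷ 19). No overlap 1.5^(10/19) = 1.24; free mixing 1.5^(6/19) = 1.14; last four last 1.5^(2/19) = 1.04.
- Step: 1.5^(share of B after the step − share of A after it). No overlap, at the arm switch: 1.5^(1 − 0) = 1.50. With overlap, when Arm B opens: 1.5^(1 − 0.4) = 1.28. Free mixing, at mid-enrolment: 10/14 of B and 4/14 of A's places are expected after the step, so 1.5^(0.714 − 0.286) = 1.5^0.429 = 1.19.

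**Share of simulated trials with p < 0.05 and no dose effect**, per comparison (300,000 replicates per cell, Monte Carlo error at most 0.1 point):

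| Schedule, 1.5-fold change | Log-SD 0.4 | 0.6 | 0.8 |
|---|---|---|---|
| n = 10, no overlap, step at arm switch | 52.4% | 26.6% | 16.4% |
| n = 10, no overlap, gradual | 17.3% | 9.9% | 7.6% |
| n = 10, free mixing, step when B opens | 18.5% | 10.9% | 8.1% |
| n = 10, free mixing, step at mid-enrolment | 10.9% | 7.5% | 6.2% |
| n = 10, free mixing, gradual | 8.4% | 6.1% | 5.3% |
| n = 10, last four last, step when B opens | 18.4% | 10.8% | 8.1% |
| n = 10, last four last, gradual | 3.9% | 4.2% | 4.3% |
| n = 10, blocks of 4, step | 2.8% | 3.6% | 3.9% |
| n = 10, blocks of 4, gradual | 3.4% | 4.0% | 4.1% |
| n = 6, step | 30.5% | 15.6% | 10.4% |
| n = 6, gradual | 11.2% | 7.3% | 5.8% |
| n = 6, blocks of 4, step | 3.0% | 3.5% | 3.7% |
| n = 6, blocks of 4, gradual | 3.4% | 3.7% | 3.9% |

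For a smaller, 1.25-fold change at n = 10, free mixing with gradual drift gives 5.5%, 4.9% and 4.7%, close to nominal. The no-overlap step gives 19.2%, 10.7% and 7.8%.

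**Power for a true 2-fold ratio, n = 10.** With no drift: 93.6%, 63.6%, 40.7%. With an opposing 1.5-fold change:
- free mixing, gradual: 78.3%, 45.2%, 28.1%
- free mixing, step when B opens: 55.7%, 29.5%, 18.6%
- no overlap, gradual: 66.2%, 34.8%, 21.5%
- no overlap, step: 29.3%, 15.2%, 10.3%
- blocks of 4: 91.9%, 61.8%, 39.6% (gradual) and 88.3%, 58.6%, 37.9% (step).

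**The case against.** The strongest reply is that no document shows any drift, so the harm is conditional. The trial is also standardised in ways that limit drift. There is one clinic, the doses before both primary biopsies are given there after an overnight fast, biopsies are nominally at 24 ± 2 hours, the first vaginal/cervical biopsy is timed to the menstrual cycle, and the rectal site and method are fixed. The target is 10 per group, and with overlap and gradual drift the false-positive rate is close to nominal. The 52% figure needs a 1.5-fold step exactly at the arm switch, no overlap and the smallest assumed spread. Drift in the direction of the dose would raise power, for example to 53–98% under gradual drift with free mixing. A null of no dose effect is also a limited yardstick when one arm takes twice the dose. Finally, the schema figure is not visible and could hold a reason for the order, and assay batching is inferred from silence.

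Much of this stands. The high figures are worst cases, the apparent ratio is more informative than the false-positive rate, and batch is only a possibility. It does not remove the point. Standardisation limits handling drift but not a change in who is recruited, and section 6 does not count procedures outside the visit windows as deviations. Power gained from drift is still bias. The minimum of 6, where overlap is impossible, is an accepted outcome of the plan. On the possible hidden reason, the visible text makes the opening of Arm B depend only on a head count, and section 3 reports that 200 mg has already been studied in a pilot. If a reason exists, it needs only to be stated.

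**Conclusion.** The concern holds. Assignment by enrolment order is explicit, it affects all four primary comparisons, and stratification by sex cannot undo it. Dose and period are fully confounded at 6 per group, and partly or fully at 10, depending on an overlap rule that the visible text does not give.

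The size of any bias cannot be known from the documents. Under an assumed 1.5-fold change at n = 10, the apparent dose ratio is 1.04 to 1.28 if the arms overlap and 1.24 to 1.50 if they do not. False-positive rates range from about 4% to 52% across the assumed drift patterns and log-SDs of 0.4 to 0.8. Blocked randomisation gives a ratio of 1.00 and 3–4% throughout. Confidence is high that the comparisons are exposed to time trends. Whether a trend will occur is unknown. This should be fixed, because the protection is cheap and the exposed contrast is the entire primary objective.

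**What to change.** Replace the sequential-assignment sentences in section 6 with wording such as:

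> Participants will be randomised 1:1 to 100 mg or 200 mg in permuted blocks of 4 within sex assigned at birth; the list is held by the IDS pharmacist.

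Blocks of 4 fit both the minimum (12 per sex, 3 blocks) and the target (20 per sex, 5 blocks). Add:

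> Each CDC assay run will contain stored specimens from both arms.

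If the sponsor has a reason for the sequence, keep it but state the reason in section 6, say whether the arms may overlap, still require mixed-arm assay runs, and report the dose comparison as non-randomised.

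The cost is a protocol amendment and a randomisation list, with no extra participants, visits or specimens. Under randomisation both dose packages are open from the start. If the sequence is kept, Arm A specimens must wait in storage until Arm B specimens exist before mixed runs are possible.
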